**Table 1: Expected number of interviews conducted with three distinct groups of antepartum and postpartum women**

Group	Antepartum	Postpartum
Adherent PrEP maternal participants	10	10
Non-adherent PrEP maternal participants	10	10
Maternal Participants who decline PrEP	10	10

Study staff members at each site will conduct IDIs with up to 60 young women. These interviews will be audio-recorded, transcribed and translated to English for analysis. With as many as ten respondents in each of the six strata, the protocol team expects saturation/redundancy to be reached. To monitor the sampling, each site will be allotted two to three slots per cell at a time, with additional slots opened as needed. If challenges arise with recruiting the targeted number of women from each site, adjustments may be made to the sampling frame by allowing other sites to enroll additional participants. Such adjustments will be done in a manner that allows for the overall target sample size to be reached within each stratum, and provides the desired representation or experiences across PrEP use and pregnancy status.

All maternal participants enrolled in the PrEP Comparison Component of this study are eligible to complete the qualitative evaluations. However, determination of adherence will need to be assessed for maternal participants of Cohort 1 who are included. For enrollment purposes, adherence/non-adherence will be defined as either achieving or not achieving target TFV-DP levels measured by DBS (which will be defined following the PK phase):

- Currently pregnant: At two consecutive antepartum visits
- Postpartum: At both the Week 6 and Week 14 visits

Maternal participants will be identified and solicited for participation by site study team members until each cell ([Table 1](#)) is complete. The interview will be conducted after written informed consent is provided.

The interviews of participants identified for the "currently pregnant" strata will take place at or after the Week 12 visit and prior to Labor and Delivery (Cohorts 1 and 2). For the postpartum groups, because selection of Cohort 1 maternal participants will depend on the DBS results from

the Week 14 visit, the interview may take place following the Week 14 visit through to and including the Week 26 visit. Women selected for the postpartum group from Cohort 2 may have their interviews anytime at or after the Week 14 visit through to and including the Week 26 visit. Interviews may be scheduled to take place at a regular study visit or an alternative date.

The interviews will be conducted by study staff members at each site who will be trained in conducting the qualitative interview. Following the training, interviewers will practice conducting digitally recorded in-depth interviews with mock participants. Through the application of the interview guide, these interviews will identify the individual, social, and structural barriers and facilitators to PrEP uptake during pregnancy, and experiences with PrEP adherence (adequate and below adequate) during pregnancy and postpartum. The interview guide will be developed with input from the qualitative interviewers at the sites to ensure that the guide is both geographically and culturally appropriate.

### **3.2.2 Exploratory Objective for PrEP Comparison Design**

The microbiome exploratory objective will assess whether PrEP alters the maternal and subsequently the infant microbiome. The samples for this objective will be collected during the regularly scheduled study visits - Entry, late pregnancy, and Weeks 6 and 26 postpartum - during the PrEP Comparison Component and will include maternal vaginal and optional rectal swabs. The Entry sample will serve as a baseline microbiome for the maternal participant during pregnancy. The re-sampling at 12 weeks will determine if the microbiome has changed significantly on FTC/TDF PrEP; pregnant women who decline PrEP will serve as the control group. The six-week postpartum time point will allow assessment of the microbiome composition after childbirth in women receiving or not receiving FTC/TDF PrEP. Finally, the 26-week postpartum time point will determine if the microbiome changes once pregnancy is over.

Infant rectal swabs or fresh stool will be collected at each timepoint to characterize the changes over time of the infant gut microbiome and potential changes resulting from exposure to maternal FTC/TDF PrEP. Changes in the microbiome will be assessed as described in [Section 9](#).

### **3.3 Standard of Care**

Sites will ensure that all participants access a basic standard of care (SOC) package which will generally include: a) HIV testing and risk reduction counseling at all visits; b) counseling and provision of contraception options; c) STI testing at screening, and STI testing and presumptive syndromic STI treatment, as needed; d) information on proper use of male and female condoms, including condom demonstrations, and provision of condoms; e) pregnancy testing; and f) discussion of HIV testing and prevention for their sexual partner(s) and referrals to local testing options for their partners. Refer to [Section 5.3.2](#) for additional details on counseling procedures.

At all visits, participants presenting with physical signs or symptoms, consistent with an STI will be referred for or provided with treatment as indicated. Participants with a laboratory diagnosis consistent with an STI will be referred for or provided with treatment as indicated. Due to the timing of specific lab testing, this may occur as an interim visit.

## 4 STUDY POPULATION

This study will be conducted among approximately 390 women and their infants (40 in the PK Component, and 350 in the PrEP Comparison Component) who will be selected for the study according to the criteria in [Sections 4.1 - 4.4](#). The study-specific approach to recruitment, screening, and enrollment is described in [Section 4.5](#). Considerations related to participant retention and withdrawal from the study are provided in [Sections 4.6](#) and [4.7](#), respectively.

### 4.1 PK Component (Groups 1 and 2)

#### 4.1.1 Inclusion Criteria

Mothers must meet all the following criteria prior to study entry to be included in this component.

**4.1.1.1** At study entry, mother is 16-24 years of age.

- *For mothers who are of legal age to provide independent informed consent as determined by site SOPs and consistent with site IRB/EC policies and procedures:* The mother is willing and able to provide written informed consent for her and her infant's study participation.
- *For mothers who are not of legal age to provide independent informed consent.* The parent/guardian or other legally authorized representative of the mother and her infant is willing and able to provide written informed consent for the mother and her infant's study participation; in addition, when applicable the mother is willing and able to provide written assent for her and her infant's study participation.

**4.1.1.2** At screening, evidence of a viable singleton pregnancy (Group 1 only) with sonographic confirmation\*

*\*Note: If adequate sonographic results are not available from medical records at screening, an ultrasound must be performed so that the result is available at study entry.*

**4.1.1.3** At study entry, pregnant or recently delivered, in one of the following two enrollment windows:

- Group 1: Gestational age of 14 to 24 weeks, defined as greater than 13 weeks plus six days and less than 24 completed weeks of gestation with sonographic confirmation\*, or
- Group 2: 6 to 12 weeks postpartum, defined as between 42 and 84 days after the date of delivery.

*\*Note: If adequate sonographic results are not available from medical records at screening, an ultrasound must be performed so that the result is available at study entry.*

- 4.1.1.4** At study entry, willing to initiate once-daily oral PrEP and continue use for at least 12 weeks under directly observed therapy and support for adherence.
- 4.1.1.5** Within 14 days prior to study entry, HIV negative by HIV RNA test.
- 4.1.1.6** At study entry, rapid test negative and absence of symptoms of acute HIV infection (i.e. acute viral illness).
- 4.1.1.7** At screening, Hepatitis B negative by Hepatitis B surface antigen test.
- 4.1.1.8** At screening, has the following laboratory test results:
  - Grade 1 or normal ( $<2.5 \times \text{ULN}$ ) ALT
  - Grade 1 or normal ( $\geq 9.5 \text{ g/dL}$ ) hemoglobin
  - Grade 1 or normal ( $\geq 800 \text{ cells/mm}^3$ ) absolute neutrophil count (ANC)
  - Normal ( $\geq 90 \text{ mL/min}$ ) estimated creatinine clearance (CrCl; Cockcroft-Gault formula)
- 4.1.1.9** At screening, mother has negative or trace proteinuria (less than Grade 1).
- 4.1.1.10** At screening, mother has normal dipstick urine for glucose (less than Grade 1).
- 4.1.1.11** At study entry, mother weighs  $> 35 \text{ kg}$ .
- 4.1.1.12** Intention to stay within the study site's catchment area for at least 12 weeks (or through delivery).

#### **4.1.2 Exclusion Criteria (PK Component and PrEP Comparison Component)**

Mothers must be excluded from the study if any of the following are identified at any time prior to study entry:

- 4.1.2.1** Mother has any current significant uncontrolled, active or chronic disease process that, in the judgment of the site investigator, would make participation in the study inappropriate.
- 4.1.2.2** Mother has a known history of any of the following, as determined by the site investigator or designee based on maternal report and available medical records:
  - Sickle cell anemia (excluding sickle cell trait), chronic bleeding, blood transfusion within the past 120 days (excluding for chronic illness) or other blood dyscrasias
  - Bone fracture not explained by trauma
  - Allergy/sensitivity to FTC/TDF or its components
- 4.1.2.3** Fetus has a known or suspected major congenital anomaly, from chart review of prior data, defined as a structural malformation with surgical, medical, or cosmetic importance

- 4.1.2.4** Mother has confirmed renal insufficiency, a history of known renal parenchymal disease, or known single kidney at screening
- 4.1.2.5** Current use of prohibited medications listed in [Section 5.5](#)
- 4.1.2.6** Concurrent participation in a study of any biomedical HIV prevention intervention or investigational drug in an HIV vaccine study or microbicide study
- 4.1.2.7** Past participation in an HIV vaccine study
- 4.1.2.8** Currently taking a PrEP regimen from non-study sources
- 4.1.2.9** Any other condition or adverse social situation that, in the opinion of the site investigator, would preclude informed consent, make study participation unsafe, complicate interpretation of study outcome data, or otherwise interfere with achieving the study objectives
- 4.1.2.10** Past participation in IMPAACT 2009

## **4.2 PrEP Comparison Component (Cohorts 1 and 2)**

### **4.2.1 Inclusion Criteria**

Mothers must meet all the following criteria prior to study entry to be included in this component.

- 4.2.1.1** At study entry, mother is 16-24 years of age.
  - *For mothers who are of legal age to provide independent informed consent as determined by site SOPs and consistent with site IRB/EC policies and procedures:* The mother is willing and able to provide written informed consent for her and her infant's study participation.
  - *For mothers who are not of legal age to provide independent informed consent.* The parent/guardian or other legally authorized representative of the mother and her infant is willing and able to provide written informed consent for the mother and her infant's study participation; in addition, when applicable the mother is willing and able to provide written assent for her and her infant's study participation.
- 4.2.1.2** At screening, evidence of a viable singleton pregnancy with gestational age of 32 weeks or less, defined as 224 days or less after the date of conception with sonographic confirmation \*
- 4.2.1.3** Within 14 days prior to study entry, negative by HIV RNA test.

*\*Note: if adequate sonographic results are not available from medical records at screening, an ultrasound must be performed in the interim so that the result is available at study entry.*

**4.2.1.4** At study entry, HIV rapid test negative and absence of symptoms of acute HIV infection (i.e. acute viral illness).

**4.2.1.5** At screening, Hepatitis B negative by Hepatitis B surface antigen test performed.

**4.2.1.6** At screening, has the following laboratory test results:

- Grade 1 or normal ( $<2.5 \times \text{ULN}$ ) ALT
- Grade 1 or normal ( $\geq 9.5 \text{ g/dL}$ ) HB
- Grade 1 or normal ( $\geq 800 \text{ cells/mm}^3$ ) ANC
- Normal ( $\geq 90 \text{ mL/min}$ ) for estimated creatinine clearance (CrCl; Cockcroft-Gault formula)

**4.2.1.7** At screening, mother has negative or trace proteinuria (less than Grade 1).

**4.2.1.8** At screening, mother has normal dipstick urine for glucose (less than Grade 1).

**4.2.1.9** Intention to stay within the study site's catchment area through 26 weeks postpartum

**4.2.1.10** Regular access to a cellular phone that is able to receive SMS messages, and for Cohort 1 only, is also able to send SMS messages.

**4.2.1.11** *Cohort 1 only:* At study entry, expresses willingness to take PrEP from pregnancy up to 26 weeks postpartum  
*Cohort 2 only:* At study entry, expresses unwillingness to take PrEP from pregnancy up to 26 weeks postpartum

**4.2.1.12** At study entry, mother weighs  $> 35 \text{ kg}$

**4.2.1.13** Based on site investigator assessment at screening, mother is literate in one or more of the study languages

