## 3.2 PrEP Comparison Component Study Design

The PrEP Comparison Component will assess feasibility, acceptability, adherence to, and safety of PrEP during pregnancy and postpartum in HIV-uninfected adolescents and young women. Women will be enrolled prior to 32 weeks' gestation in two cohorts: those who agree to initiate PrEP (Cohort 1) and those who decline (Cohort 2). Infants will be enrolled *in utero* at the same time the woman is enrolled. A randomized trial in which one arm would not receive PrEP would be unethical at this time due to the overwhelming evidence supporting the efficacy of PrEP to prevent HIV infection (172). All women enrolled in the study will receive a standard of care package of HIV prevention services and a study-specific behavioral risk reduction intervention. Additionally, all women will receive support for antenatal, delivery and early infant care through

one-way mHealth messaging services. Women who choose to initiate PrEP will be provided PrEP as well as a study-specific adherence support intervention.

Regardless of cohort, all maternal participants will follow similar schedules of evaluations through the course of pregnancy and in the 26 weeks following delivery. Following Cohort 2 provides an opportunity to document the process of decision-making around HIV prevention during this time of substantial risk; as these women may choose to initiate PrEP at any stage following study entry, triggers for change in PrEP perceptions and acceptability over time will be recorded to better understand women's motivation to seek additional HIV prevention (see [Section 3.2.1](#)) services. As Cohort 2 is not exposed to antiretroviral agents during pregnancy or postpartum, the study will also obtain preliminary safety data for TDF use in HIV-uninfected women during this period. Cohort 2 will serve as a comparison group for estimates of incidence and prevalence of maternal and infant safety outcomes including a) pregnancy outcomes, b) maternal adverse events, and c) infant growth and development between the two cohorts (see [Section 9.2.2](#)). The primary analysis will be based on original Cohort designation at baseline. Additional secondary analyses that consider the population of women who may initially decline PrEP and then later decide to initiate it will be considered, refer to [Section 9](#).

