## 6.2 PrEP Comparison Component

### 6.2.1 PrEP Comparison Component Maternal Screening, Enrollment and Follow-up Visits

Refer to [Section 4.5](#) for a description of the study recruitment, screening, and enrollment process. Women will be evaluated for potential participation with a gestational age that will permit study enrollment before 32 completed weeks. Infants will enroll into the PrEP Comparison Component, *in utero*, at the time their mothers enter the study. Infants will have study visits at birth, and 6, 14 and 26 weeks after birth.

Screening may be initiated after informed consent is obtained. All screening procedures except for sample collection for HIV RNA are expected to be performed within 30 days prior to study entry. Screening evaluations may be repeated during the 30-day period, with the latest outcomes used for eligibility determination. A HIV negative NAT test result, from a specimen collected within 14 days prior to enrollment, is required prior to entry. Multiple screening visits may be conducted within the 30-day time frame to complete all required procedures. If the 30-day screening period is exceeded, the screening process may be repeated. For potential participants who do not meet the eligibility criteria, screening may be discontinued once ineligibility is determined.

- Maternal creatinine testing is required in relation to the eligibility criteria in [Section 4.1.2.4](#) and to select follow up and step change visits; as soon as the creatinine test result is obtained for a given visit, the estimated CrCl rate should be calculated using the Cockcroft-Gault formula, and all results should be graded for severity as specified in [Section 7.2.1](#), and assessed for clinical significance concurrent with all other laboratory test results.

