### 6.2.1.1 PrEP Comparison Component Maternal Enrollment Visit

For eligible women, enrollment must occur in time for study drug initiation prior to 32 completed weeks of gestation. The point of enrollment is taken to be the time when a participant has successfully been entered in the Subject Enrollment System (SES). All Entry Visit procedures are expected to be performed on the day of enrollment; procedures that may provide information relevant to eligibility for the study (e.g., rapid HIV test, medical history, physical examination), should be performed first prior to final eligibility determination and assignment to a study cohort. If a participant is found to be ineligible on the day of enrollment, enrollment should not occur.

Additional requirements for sequencing of procedures at the Entry Visit are as follows:

- Rapid HIV testing, and final eligibility determination and confirmation must precede enrollment.
- For women in Cohort 1:
  - Enrollment must precede prescribing of study drug.
  - Study drug prescribing must precede dispensing.
  - Blood collection for baseline TFV-DP drug level evaluation must precede ingestion of study drug.

PrEP Comparison Component Maternal Enrollment Visit Procedures (Day 0)	
Administrative and Regulatory	

• Complete final eligibility determination and confirmation

• Complete eligibility checklist, enter checklist data into SES to enroll the participant, print and file a copy of the confirmation

• Collect comprehensive locator information

Behavioral and Counseling	

• iNSC [see Section 5.3.2 for specific counseling for each cohort]

• CASI and COVID-19 questionnaire [see Section 6.16]

Clinical	

• Update medication and medical history since last visit

• Perform complete maternal physical exam

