2.1.2 PrEP Comparison Component Study Design

The IMPAACT 2009 PrEP Comparison Component is a parallel observational cohort study. It will assess feasibility, acceptability, adherence to, and safety of PrEP during pregnancy and in the postpartum period among adolescents and young women who are HIV-negative. Women will be screened prior to 32 weeks' gestation and subsequently enrolled in two cohorts: those who choose to initiate PrEP at enrollment (Cohort 1) and those who decline (Cohort 2). Infants will be enrolled *in utero* at the same time the woman is enrolled. A randomized trial in which women were assigned to an arm that would not receive PrEP would be unethical at this time due to the overwhelming evidence supporting the efficacy of PrEP to prevent HIV infection. All women enrolled in the study will receive a standard of care package of HIV prevention services and a study-specific behavioral risk reduction intervention. Additionally, all women will receive support for antenatal, delivery and early infant care through brief motivational-interviewing informed counseling at each study visit and one-way mHealth messaging services. Women who choose to initiate PrEP will be provided PrEP as well as drug-level informed adherence support intervention.

Approximately 350 women will be enrolled to achieve at least 300 evaluable women (200 in Cohort 1 and 100 in Cohort 2) and their infants, defined as completing the week 26 postpartum visit. Women will be accrued over a 12-month period (from the date of first enrollment) and followed through 26 weeks postpartum. For each woman, the duration of follow-up is expected to range from seven to 12 months depending on gestational age at entry. For each infant, the expected duration of follow-up is approximately six months.

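### Eligibility criterion 4.2.1.2 counts its 32-week limit from conception and applies it at screening, so it does not match the under-32-week cap at enrollment set in Protocol Sections 3.2, 6.2.1 and 6.2.1.1

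*Protocol*

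**What the plan says.** The documents state the gestational-age limit for the PrEP Comparison Component in several places:

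- **Protocol 4.2.1.2 (inclusion criterion).** The time point is screening: "At screening, evidence of a viable singleton pregnancy with gestational age of 32 weeks or less". The limit is then turned into days: "gestational age of 32 weeks or less, defined as 224 days or less after the date of conception".
- **Protocol 3.2 (design).** The time point is enrollment: "Women will be enrolled prior to 32 weeks' gestation in two cohorts".
- **Protocol 6.2.1 (screening and follow-up).** "Women will be evaluated for potential participation with a gestational age that will permit study enrollment before 32 completed weeks".
- **Protocol 6.2.1.1 (enrollment visit).** For eligible women, "enrollment must occur in time for study drug initiation prior to 32 completed weeks of gestation".
- **SAP 2.1.2.** "Women will be screened prior to 32 weeks' gestation and subsequently enrolled in two cohorts". No limit at enrollment is given.

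The gap between screening and entry is set in Protocol 6.2.1: "All screening procedures except for sample collection for HIV RNA are expected to be performed within 30 days prior to study entry".

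The PK Component criterion (Protocol 4.1.1.3) is written differently. It counts completed weeks of gestation, applies at study entry and does not mention conception.

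**The concern.** The passages differ on three things.

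1. **Scale.** The criterion names gestational age but starts the count at conception. On the usual convention, gestational age starts about two weeks before conception, so the same 224 days reach a later point in pregnancy.
2. **Time point.** The criterion and the SAP test the limit at screening. Protocol 3.2, 6.2.1 and 6.2.1.1 test it at enrollment, up to 30 days later.
3. **Boundary.** The criterion includes day 224. A limit of before 32 completed weeks excludes it.

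This matters because Protocol Section 4 says women are selected by the criteria in Sections 4.1 to 4.4, and Section 4.5 says enrollment happens when the required eligibility data are entered in the enrollment system. That list contains no gestational-age limit at entry.

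Late entrants would weaken two primary estimands. Antepartum drug levels feed the adherence estimand (SAP 6.3.1), and preterm delivery is a component of the pregnancy-outcome composite (SAP 6.3.3). The cohorts are self-selected, and Protocol 9.2.5 itself warns that large cohort differences in gestational period at enrollment could introduce bias.

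**Working it through.** **The plan's own figure.** 224 / 7 = 32.0 weeks. The day count is right for 32 weeks; only its starting point is in question.

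**Inputs from the documents.** Limit of 224 days (Protocol 4.2.1.2). Up to 30 days from screening to entry (6.2.1). Preterm means before 37 completed weeks, so before day 259 (9.2.2.1). Follow-up ends 26 weeks, or 182 days, after delivery. Expected follow-up is seven to 12 months (Schema; SAP 2.1.2).

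**Assumptions, not in the documents.** Offset from gestational day 0 to conception: 14 days by the usual convention, or 0 if the criterion uses conception loosely for gestational day 0. Delivery at 40w0d (day 280). One month = 30.4375 days, so seven months is 213 days.

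**Formulas.** Latest entry = latest screening day + 30. Week 4 target = entry + 28. Days at risk of preterm delivery = 259 − entry, not below 0. Follow-up = (280 − entry) + 182.

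| Reading | Latest screening | Latest entry | Week 4 target | Days at risk of preterm delivery | Follow-up |
|---|---|---|---|---|---|
| 6.2.1.1 cap at entry | not the limiting step | 223 d = 31w6d | 251 d = 35w6d | 36 | 57 + 182 = 239 d = 7.9 months |
| SAP 2.1.2 wording alone | 223 d = 31w6d | 253 d = 36w1d | 281 d = 40w1d | 6 | 27 + 182 = 209 d = 6.9 months |
| 4.2.1.2 alone, offset 0 | 224 d = 32w0d | 254 d = 36w2d | 282 d = 40w2d | 5 | 26 + 182 = 208 d = 6.8 months |
| 4.2.1.2 alone, offset 14 | 238 d = 34w0d | 268 d = 38w2d | 296 d = 42w2d | 0 | 12 + 182 = 194 d = 6.4 months |

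**Antepartum drug levels.** The entry sample is taken before the first dose, so Week 4 is the first on-drug sample. Its window is ±7 days (6.2.1.2). For entry at 36w1d the window opens at 253 + 21 = 274 d = 39w1d, so one antepartum sample is still possible. For entry at 38w2d it opens at 268 + 21 = 289 d = 41w2d. Even with the ±14 days of Appendix X it opens at 268 + 14 = 282 d = 40w2d, after a 40-week delivery.

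**Follow-up.** The shortfall against 213 days is 4 or 5 days at about 36 weeks (209 or 208) and 19 days at 38w2d (194).

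**Which reading the design figures fit.** Entry at 32w0d gives 56 + 182 = 238 d = 7.8 months, with Week 4 at 36w0d and Week 8 at 40w0d. That agrees with the seven-month minimum. It also agrees with Section 6.2.1.2, which provides for delivery before the Week 8 or Week 12 visit but not before Week 4.

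**The case against.** The strongest reply is that 4.2.1.2 is a necessary condition, not the only one. Section 6.2.1.1 is a separate mandatory rule, 6.2.1 repeats it and 3.2 applies it to both cohorts. Section 6.2.1.1 also says that a woman found ineligible on the day must not be enrolled. This stands. A reader might infer from 4.2.1.2 that the protocol admits women at 34 or 38 weeks; taken as a whole, it does not.

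Second, the reference to conception looks like a drafting slip. 224 is exactly 32 × 7, sonographic confirmation is required, and the ultrasound report in Section 6.15 records gestational age or estimated delivery date, with no conception date. The Schema and the SAP target populations use weeks of gestation. This makes the 14-day reading less likely in practice, but it does not touch the timing problem. With offset 0, the criterion alone still allows entry at 36w2d.

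Third, some harms that a reader might add do not follow from this wording. No woman entering at 20 weeks or later can have a spontaneous abortion as defined (before 20 weeks); that comes from the intended design. Late entry also leaves the labor-and-delivery and postpartum drug levels intact.

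Fourth, gestational timing is already watched. Enrollment is stratified by trimester, and the Clinical Management Committee monitors cohort balance (Protocol 9.2.3 and 9.2.5). That helps, but a single third-trimester stratum does not separate entry near 31 weeks from entry at 36. Nothing in the documents shows that late entry would differ between cohorts, so bias is a possibility and not a finding.

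**Conclusion.** Wrong as written, and worth correcting. Criterion 4.2.1.2 is mis-anchored and mis-timed relative to Sections 3.2, 6.2.1 and 6.2.1.1; SAP 2.1.2 shares the timing problem; and the boundary differs by a day. The protocol as a whole caps enrollment below 32 weeks. The exposure is that a site using only the eligibility list, or the SAP wording, could pass women whom 6.2.1.1 excludes.

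The size is entry up to about 36 weeks on the gestational scale. The 38w2d figure needs three things together: 4.2.1.2 read alone, an assumed 14-day offset, and the full 30-day window. It should not be quoted as what the protocol permits. At about 36 weeks the loss is most of the antepartum drug-level data and all but five or six days at risk of preterm delivery; the follow-up shortfall is only a few days and depends on the assumed 40-week delivery. No power, sample-size or alpha figure depends on this point.

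**What to change.** Reconcile Protocol 4.2.1.2, 3.2, 6.2.1 and 6.2.1.1 and SAP 2.1.2 to:

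- **One scale:** ultrasound-derived gestational age in weeks and days, with the reference to conception removed from 4.2.1.2.
- **One time point:** the stated seven-to-12-month follow-up and the antepartum visit schedule fit a limit at study entry, which the three protocol sections already use. Put that limit in the eligibility list itself.
- **One boundary:** say whether 32w0d is in or out, and use the same form in the Schema and the SAP target populations.

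The PK criterion in 4.1.1.3 is a ready model for the scale and time point. The cost is a short clarification in each document and a check that the eligibility checklist matches. It removes no one whom Section 6.2.1.1 would have allowed, except that the team must settle the single day at 32w0d.
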